5.1.6. Will this study bank data and/or specimens? **YES**

5.1.6.1. **If yes, include information on data and specimen banking.**
Coded plasma samples not exhausted in measuring BDNF will be stored in

5.1.6.2. **IF BANKING SPECIMENS, IT MUST BE AT A VA APPROVED FACILITY.**
(For additional information, go to the following website http://www.research.va.gov/programs/tissue_banking/, or contact the IRB office.)

5.1.6.3. **If specimens will be banked, specify banking location.**
Coded Specimens will be stored in alarmed freezers within a locked laboratory in Building 21 Lab A405. Only appropriate personal have access to the specimens. The freezers have alarm settings to monitor temperature (high alarm at -70C, low alarm at -90C). Freezers are equipped with an alarm that will sound if the freezers' temperature is compromised.

5.1.6.4. **If the location is a non-VA site, has the mandatory approval from VA Central Office been obtained through submission of a tissue banking application? Choose an item.**

5.1.6.4.1. **If yes, provide a copy of the response from VA Central Office.**

5.1.6.5. **If applicable, explain how destruction of banked samples will be substantiated.**

5.1.6.6. **Do you anticipate using the banked specimens for other studies beyond the defined study period and defined study parameters? YES**

5.1.6.6.1. **If yes, will you need to re-contact subjects? How will this be done?**

Banking and potential future use of specimens will be detailed during the informed consent process. Subjects will not be re-contacted.

5.2. **Participant Recruitment Methods**

5.2.1. **State how many subjects will be needed.**
We will screen approximately 250 subjects with brief olfactory testing. We anticipate about 120 subjects with abnormal olfactory testing will undergo baseline assessment including DAT-SPECT as described above. We will randomize 88 subjects to either exercise intervention or no intervention and anticipate that 70 subjects will complete all aspects of the study. 2018 Amendment: We anticipate enrolling 56 additional subjects under the modified inclusion criteria with 48 (24 per group) expected to complete all study activities.

5.2.2. **Who will be responsible for recruiting potential participants? Provide titles of individuals.**

After referral from providers (see below), recruitment will be coordinated by the study coordinator or one of the study PI or co-Is

5.2.3. How will initial contact with potential participants be made? (e.g., local clinics, physician referrals, letters to prospective participants) *NOTE: VA policy prohibits "cold calls" to potential VA research participants. Provide an introductory letter and telephone script.* Additionally, letters will be sent to potential participants letting them know that they may be eligible for a study with a brief description of the study and give them a number of they would like to learn more or to request no further contact.

The potential subjects will be identified by their treating psychiatrist or neurologist. Subjects will be initially told about the study by their primary psychiatrist or neurologist emphasizing that participation is entirely voluntary and will not affect their clinical care. Those subjects that express interest will meet with the study PI, co-PI or research staff to receive detailed information about the study. Potential subjects with DIP will be pre-screened using a brief (12 item) scratch and sniff smell test with hyposmic subjects invited to learn more about the study (see script). Brief olfactory testing should be completed in 5-10 minutes. Hyposmic subjects will be asked if they wish to they proceed with informed consent. In addition to the screening described above, we will invite subjects from [name] CPPF pilot study "Degenerative nigrostriatal dysfunction in drug-induced parkinsonism" PROM#01481 who have abnormal DaT-SPECT to enroll in the present protocol. These subjects will have explicitly agreed to future contact for related studies in the ICF for PROM#01481. We may also invite subjects identified by their PADRECC provider who had DaT-SPECT (with an abnormal result) performed clinically outside of a research protocol within the prior 3 months and agree to be contacted. In addition to recruiting directly from clinics as above, we will obtain a list of patients prescribed medications associated with DIP in the last 12 months using the CACs or Clinical Pharmacy Database (with the ability to re-query every 4 months for new drug starts). This list will contain only names, last 4 SSN digits and medication prescribed without other clinical information and will be transmitted through encrypted email using a password protected spreadsheet. The list will be used to identify CPRS charts for screening under the conditions of our HIPAA waiver (rather than blindly screening all charts with a Behavioral Health appointment). We will contact providers of potentially eligible active or control subjects such that initial contact about the study will come through their clinical providers. Additionally, letters will be sent to potential participants letting them know that they may be eligible for a study with a brief description of the study and give them a number of they would like to learn more or to request no further contact. Subjects with a clinical diagnosis of PD will be directly referred by their PADRECC provider.

5.2.4. Will you be using any of the following methods to recruit participants? (Check all that apply.)

- N/A**
- Local database for which participants have NOT given prior permission to be contacted for Research.** *NOTE: If this option is checked, please submit a Waiver of Individual Authorization for Disclosure of Protected Health Information.*
- Personal contact with patients over whom you have direct/indirect oversight**
- Provider (Clinician) Referrals of potential participants**

5.2.5. Indicate the types of recruitment/advertisement materials that will be used: Check all that apply. Submit copies of recruitment materials, for IRB review.

Not applicable; none to be used
 Fliers Newspapers Letters Websites Television
 Radio Audio Video Surveys

Other (Specify, e.g. employee newsletters)

5.2.6. Participants will be given a copy of the Notice of Privacy Practice. YES

5.3. **Compensation for Participation** - YES If yes, complete the following.

5.3.1. Summarize any financial compensation that will be offered to subjects.

• Subjects will paid \$50 for completion of each of the study visits (baseline assessment including DAT-SPECT and each of three assessments including fitness and motor testing. Results of the brain scan will not be known before conclusion of the baseline visit, thus all patients (regardless of normal/abnormal scan results) will be asked to provide a blood sample and all will be paid.

5.3.2. Provide the schedule for compensation.

5.3.2.1. Per study visit or session.

\$50 for each baseline visit (VA and exercise), \$20 for the 8-week visit and
\$50 for each completion visit (VA and exercise)

5.3.2.2. Total amount for entire participation.

\$220

5.3.3. State how compensation will be provided: : Check

Compensation will be provided in check form after the visit. The check will be mailed to the patient's home address.

5.4. Informed Consent Procedures

5.4.1. Indicate if informed consent will be obtained and/or if you are requesting a waiver of informed consent or waiver of documentation of informed consent. Consent to be obtained

5.4.2. If the research involves multiple phases, specify for which phases of the research the waiver(s) is/are being requested.

5.4.3. Describe circumstances, if any, that may need to be addressed in seeking informed consent (e.g., subjects with impaired decision making ability and the use of a legally authorized representative, etc.)

Subjects who cannot provide their own consent will not be recruited.

5.4.4. If applicable, indicate how study personnel will be trained regarding human subjects protections requirements and how to obtain and document informed consent.

All study personnel received CMCVAMC-mandated training and obtained requisite Certificates of Completion.

5.4.5. Inclusion/Exclusion Criteria: Describe the criteria that determine who will be included in or excluded from the study.

5.4.5.1. Inclusion Criteria

We will recruit subjects with parkinsonian signs (rest tremor, rigidity, bradykinesia) occurring after the institution of therapy with a medication having a known association with DIP (examples include haloperidol, chlorpromazine, fluphenazine, perphenazine, risperidone, thioridazine, thiothixene, lithium, valproic acid, ziprasidone, olanzapine and aripiprazole). Potential subjects with DIP will be pre-screened using a brief (12 item) scratch and sniff smell test with hyposmic subjects invited to learn more about the study (see script). Brief olfactory testing should be completed in 5-10 minutes. We will also invite subjects from [name] CPPF pilot study "Degenerative nigrostriatal dysfunction in drug-induced parkinsonism" PROM#01481 who have abnormal DaT-SPECT to enroll in the present protocol. These subjects will have explicitly agreed to future contact for related studies in the ICF for PROM#01481. We may also invite subjects identified by their PADRECC provider who had DaT-SPECT (with an abnormal result) performed clinically outside of a research protocol within the prior 3 months and agree to be contacted. We will also recruit subjects with a clinical diagnosis of PD (Hoehn & Yahr (H/Y) stage ≤ 2 made by a PADRECC provider.

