AP drugs are increasingly prescribed for newly-approved indications including mood disorders and a variety of off-label uses including anxiety, mood stabilization and PTSD (20, 65, 66). For example, in a study of prescribing patterns within the VA, 168,442 of 279,778 individuals (60.2%) who received an AP had no record of a diagnosis for which the drugs were approved(20). In addition to the immediate morbidity attributable to motor symptoms in DIP, APs may act as a “stress test” for the brain revealing subclinical dopaminergic dysfunction such as prodromal PD offering the opportunity for study and

intervention at the earliest stages of disease. The study of disease-modifying therapies in general (and exercise in particular) has been limited by significant dopaminergic denervation already present at motor diagnosis of PD and lack of biomarkers to reliably measure changes in progression. The identification of a prodromal PD cohort will offer the opportunity to study exercise as a symptomatic treatment for DIP and disease-modifying therapy in PD using DaT SPECT as a symptom-independent marker of disease progression.

Section 4: Objectives Section

4.1. Describe the study's purpose, specific aims, or objectives.

AIM 1: To test the effect of regular aerobic exercise on motor function in DIP.

AIM 2: To test whether regular aerobic exercise influences disease progression in prodromal PD

AIM 3: To characterize the mechanism and biochemical correlates of exercise-induced changes in subjects with preclinical PD.

4.2. State the hypotheses to be tested.

Hypothesis 1: Short-term home exercise will improve motor function and could be an effective rehabilitation intervention in DIP.

Hypothesis 2: Exercise subjects will exhibit slower decline in quantitative DaTl, suggesting a disease-modifying effect of exercise in PD.

Hypothesis 3: The relationship of serum markers with clinical and imaging variables will suggest pathways involved in functional changes or disease modification.

Section 5: Study Procedures

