5.1. Study Design

5.1.1. Describe in detail the experimental design, i.e. from recruitment procedures to study closure.

Subjects: Patients aged 40-89 with a clinical diagnosis of DIP or PD will be recruited from the PVAMC PADRECC and Behavioral Health Service (BHS) clinics.

Inclusion criteria: We will recruit subjects with parkinsonian signs (rest tremor, rigidity, bradykinesia) occurring after the institution of therapy with a medication having a known association with DIP (examples include haloperidol, chlorpromazine, fluphenazine, perphenazine, risperidone, thioridazine, thiothixene, lithium, valproic acid, ziprasidone, olanzapine and aripiprazole). Potential subjects with DIP will be pre-screened using a brief (12 item) scratch and sniff smell test with hyposmic subjects invited to learn more about the study (see script). Brief olfactory testing should be completed in 5-10 minutes. We will also invite subjects from [name] CPPF pilot study "Degenerative nigrostriatal dysfunction in drug-induced parkinsonism" PROM#01481 who have abnormal DaT-SPECT to enroll in the present protocol. These subjects will have explicitly agreed to future contact for related studies in the ICF for PROM#01481. We may also invite subjects identified by their PADRECC provider who had DaT-SPECT (with an abnormal result) performed clinically outside of a research protocol within the prior 3 months and agree to be contacted. We will also recruit subjects with a clinical diagnosis of PD (Hoehn & Yahr (H/Y) stage ≤ 2 made by a PADRECC provider.

Exclusion criteria: 1) Subjects with a known diagnosis of, atypical parkinsonian syndromes (i.e. dementia with Lewy bodies, progressive supranuclear palsy, corticobasal degeneration, multiple system atrophy) or other neurodegenerative condition, with the exception of PD, will be excluded; 2) Subjects with a history of sinus trauma or surgery, encephalitis, current nasal congestion or other known reason for olfactory impairment will not be screened 3) Subjects with a contraindication to DaTl (sensitivity or allergy to iodine, treatment with a drug with a significant effect on DaTscan that cannot be temporarily weaned)

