Monitoring of control subjects: All subjects (control and intervention) with abnormal DaT SPECT will be referred to the PADRECC for clinical followup including usual care for monitoring of symptom progression and institution of any necessary symptomatic therapies. Study participation will not limit any aspect of routine clinical care. Importantly, levodopa and other common dopaminergic therapies do not interfere with lofupane binding to dopamine transporters and do not significantly influence DaT SPECT. Enrolled non-intervention subjects will receive similar weekly phone calls from study staff as will intervention subjects. During the weekly phone calls, staff will administer the Parkinson's Disease Questionnaire-8 (96), a short well-validated assessment of parkinsonian symptoms and quality of life that can be completed in only a few minutes. During the baseline visit, at 8 weeks and at the 52 week assessment, study staff will administer the International Physical Activity Questionnaire, a well-characterized self-report instrument that has also been used to measure physical activity in subjects with PD(97, 98), allowing monitoring of any changes in activity over the course of the intervention using paired t-tests.

Study Design:

AIM 1: To test the effect of regular aerobic exercise on motor function in DIP. In this aim, we will test the hypothesis that a short term home exercise regimen will improve motor function in DIP subjects and could be an effective rehabilitation intervention.

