Subjects/Procedures: A cohort of DIP subjects with presumed prodromal PD will be defined by a two-tiered screening procedure. First, DIP subjects will undergo olfactory testing administered by trained study personnel. Subjects with hyposmia (defined as scores below the 25th percentile for age and gender using well-established normative data for the UPSIT) on initial olfactory testing will undergo DaT imaging. We will also recruit subjects with a clinical diagnosis of PD by a PADRECC provider. SPECT scans will initially be read as normal, mildly abnormal or clearly abnormal, in accord with current clinical practice, by a nuclear medicine physician blinded to clinical status. High inter-rater agreement (kappa 0.89-0.93) has been reported for clinical reading of DaT(99). All patients with abnormal (mildly or clearly) DaT SPECT will be referred for clinical follow-up in the PADRECC. The combination of DIP, hyposmia and abnormal striatal DaT imaging will be operationally defined as prodromal PD. All subjects with abnormal olfaction and DaT deficit will undergo baseline motor testing (UPDRS motor and instrumented Timed Up and Go) together with safety screening for exercise. If eligible based on safety screening, baseline cardiovascular fitness testing (VO₂max measurement) will be obtained as described above. Subjects will be then be randomized in a 1:1 ratio to a home-based exercise intervention (5 days/week aerobic walking with confirmation by remote activity monitoring) or no intervention. Subjects will receive weekly phone calls from staff to monitor safety and compliance. After 8 weeks, subjects will undergo repeat clinical (UPDRS motor), quantitative (iTUG) and fitness testing (VO₂max) to examine short-term symptomatic effects of exercise. Eight weeks is a common duration for short-term rehabilitation interventions and was recently reported in a Phase I/II trial of aerobic walking in PD(8).

AIM 2: To test whether regular aerobic exercise influences disease progression in prodromal PD. In this aim, we will test the hypothesis that exercise subjects will exhibit slower decline in semi-quantitative striatal DaT SPECT, suggesting a disease-modifying effect of exercise in prodromal PD.

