Patients aged 40-89 with a clinical diagnosis of DIP will be recruited from the CMC VAMC PADRECC and Behavioral Health Service (BHS) clinics. We will recruit subjects with parkinsonian signs (rest tremor, rigidity, bradykinesia) occurring after the institution of therapy with a antipsychotic medication having known dopamine receptor blocking activity (examples include haloperidol, chlorpromazine, fluphenazine, perphenazine, risperidone, thioridazine, thiothixene, ziprasidone, olanzapine and aripiprazole). Potential subjects with DIP will be pre-screened using a brief (12 item) scratch and sniff smell test with hyposmic subjects invited to learn more about the study (see script). Brief olfactory testing should be completed in 5-10 minutes. We anticipate screening 250 subjects with olfactory testing. Approximately 120 subjects will undergo baseline assessment including DaT-SPECT as described above. Subjects with abnormal DaT-SPECT will be invited to be randomized into the exercise study. In addition to the screening described above, we will invite subjects from [name] CPPF pilot study "Degenerative nigrostriatal dysfunction in drug-induced parkinsonism" PROM#01481 who have abnormal DaT-SPECT to enroll in the present protocol. These subjects will have explicitly agreed to future contact for related studies in the ICF for PROM#01481. We may also invite subjects identified by their PADRECC provider who had DaT-SPECT (with an abnormal result) performed clinically outside of a research protocol within the prior 3 months and agree to be contacted. We will randomize 88 subjects to either exercise intervention or no intervention and anticipate that 70 subjects will complete all aspects of the study. Additionally, letters will be sent to potential participants letting them know that they may be eligible for a study with a brief description of the study and give them a number of they would like to learn more or to request no further contact. 2018 Amendment: We anticipate enrolling 56 additional subjects under the modified inclusion criteria with 48 (24 per group) expected to complete all study activities. This will still allow for meaningful analysis of our primary outcomes according to the sensitivity analysis of sample size from the original protocol (20 per group adequate).

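### Clinical PD patients are eligible, but the aims still speak of DIP or prodromal PD and no analysis names diagnosis; the claim that 20 per group suffices is not supported for this mixed population

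*Combined protocol and SAP*

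**What the plan says.** **Who may enter.** Section 5.1.1 opens with "Patients aged 40-89 with a clinical diagnosis of DIP or PD will be recruited". Sections 5.1.1 and 5.4.5.1 both state "We will also recruit subjects with a clinical diagnosis of PD", limited to Hoehn and Yahr stage 2 or below. Section 5.2.3 gives the route: "Subjects with a clinical diagnosis of PD will be directly referred by their PADRECC provider". The Aim 1 procedures in Section 5.1.1 also mention recruiting clinical PD.

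**Whom the aims concern.** Section 4.1 has "AIM 1: To test the effect of regular aerobic exercise on motor function in DIP". Hypothesis 1 is likewise about DIP, and the Aim 1 text in Section 5.1.1 tests whether "a short term home exercise regimen will improve motor function in DIP subjects". Aim 2 concerns prodromal PD; its text in Section 5.1.1 speaks of slower decline "suggesting a disease-modifying effect of exercise in prodromal PD" and takes the same prodromal cohort as Aim 1. That cohort is defined there: "The combination of DIP, hyposmia and abnormal striatal DaT imaging will be operationally defined as prodromal PD". Section 5.1.3 repeats the recruitment sentence without PD: "Patients aged 40-89 with a clinical diagnosis of DIP will be recruited".

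**How the data are analysed.** Allocation is 1:1 with no stratification stated. Section 9.2 compares the Aim 1 change in UPDRS motor score by a two-sample t-test. The Aim 2 mixed model names age, gender and unspecified other confounders.

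**Sample size.** Section 9.1 needs 35 per group for Aim 1 and plans on 35 per group for Aim 2. The 2018 text in Sections 5.1.3 and 9.3 expects 56 additional subjects and 48 completers (24 per group). It says this still serves the primary outcomes because 20 per group was adequate in the original sensitivity analysis.

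**The concern.** Prodromal PD, as the protocol defines it, requires DIP. A patient with clinical PD and no DIP is therefore eligible but belongs to neither the Aim 1 nor the Aim 2 population as worded. The planned tests pool everyone and estimate an average over whatever mix is enrolled. That average equals the DIP or prodromal effect only if the effect is the same in both groups, and by itself it cannot show an effect in DIP. The protocol's background treats DIP as a separate question, little studied and with a mixed levodopa response. It motivates Aim 2 by the value of intervening before manifest disease.

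The sample-size sentence has a related weakness. The figure of 20 per group depends on faster dopamine-transporter loss, argued from the possibility that prodromal loss exceeds loss in manifest PD. Enrolling manifest PD removes that argument for those patients. The sentence also refers to the primary outcomes in general, although the sensitivity analysis concerned Aim 2 only.

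**Working it through.** All power figures use a two-sided two-sample t-test (noncentral t) at alpha 0.05. Alpha is stated for Aims 2 and 3 and assumed for Aim 1.

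**1. Aim 1, the plan's own figure.** Inputs from Section 9.1: difference 5.0, SD 7.3, power 80%. Standardised difference = 5.0 / 7.3 = 0.685, which requires 34.4, so 35 per group. With 20% drop-out, 35 / 0.8 = 43.75, so 44. The plan's 35 and 44 are reproduced.

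**2. Aim 1 at the amended size.** With the same inputs, power is 0.806 at 35 per group, 0.642 at 24 and 0.560 at 20. This loss comes from the smaller sample; mixing diagnoses plays no part in it.

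**3. Aim 2, the plan's own figures.** The base case is a loss of 0.15 against 0.09, a difference of 0.06, or 0.06 / 0.15 = 40% slowing. Applying 40% to each sensitivity scenario and solving for the SD that gives 80% power:

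| Yearly loss | Difference | n per group in plan | Implied SD |
|---|---|---|---|
| 0.15 | 0.060 | 35 | 0.0883 |
| 0.165 | 0.066 | 29 | 0.0882 |
| 0.18 | 0.072 | 24 | 0.0872 |
| 0.20 | 0.080 | 20 | 0.0880 |

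The four sizes agree with one another at an SD of about 0.088. Section 9.1 prints an SD of change of 0.13. That mismatch is a separate matter, so both values are carried forward.

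**4. Aim 2 with clinical PD enrolled.** Assumptions: loss 0.20 in prodromal and 0.15 in manifest PD, 40% slowing in both, and the SD held fixed. The documents give no PD share, so a range is shown. Mixed loss = 0.20 − 0.05 × PD share; difference = 0.4 × mixed loss.

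| PD share | Difference | n for 80% (SD 0.0883) | Power, n=24 (SD 0.0883) | Power, n=20 (SD 0.0883) | Power, n=24 (SD 0.13) |
|---|---|---|---|---|---|
| 0% | 0.080 | about 20 | 0.867 | 0.797 | 0.551 |
| 25% | 0.075 | 23 | 0.821 | 0.745 | 0.499 |
| 50% | 0.070 | 26 | 0.767 | 0.686 | 0.447 |
| 75% | 0.065 | 30 | 0.704 | 0.621 | 0.396 |
| 100% | 0.060 | 35 | 0.635 | 0.553 | 0.347 |

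The last row is the plan's own base case: at a loss of 0.15 it requires 35 per group.

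**5. What the pooled Aim 1 estimate can say about DIP.** Pooled effect = PD share × PD effect + (1 − PD share) × DIP effect. As an illustration only, take 5 points in PD and 2.5 in DIP. At PD shares of 25/50/75% the pooled effect is 3.125/3.75/4.375 points, which is 25/50/75% above the DIP effect. With equal effects there is no discrepancy.

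**6. Precision of estimates by diagnosis.** Take 24 per group and PD shares of 25/50/75%, so m = 18/12/6 DIP subjects per arm. The DIP-only 95% CI half-width is t × 7.3 × √(2/m) = 4.9/6.2/9.4 points. The interaction half-width is t × 7.3 × √(2/m + 2/(24−m)) = 9.8/8.5/9.8 points, with 17–21% power for a 5-point gap.

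**The case against.** The strongest reply is that the protocol already looks beyond DIP. Hypothesis 2 concludes about disease modification in PD, the background proposes a prodromal cohort as a means to that end, the safety text expects preclinical or very early PD, and Section 5.6.3.1 says the study tests exercise in DIP and PD. This stands for Aim 2: a conclusion about PD is within the stated inference, and the difficulty is confined to a prodromal-specific claim. It does not help Aim 1, which asks about DIP.

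The Aim 1 planning effect comes from PD trials, so enrolling PD makes that assumption better supported. This also stands. A reader might infer that mixing diagnoses causes the Aim 1 power loss, or that exercise works less well in DIP. The documents support neither: the loss is due to n, and they give no effect by diagnosis.

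The unspecified other confounders could include diagnosis. Adjustment would still give an overall effect and not a DIP effect.

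Finally, the 2018 text says additional subjects. If they join those already randomised, the shortfall shrinks: 11 further completers per group (35 − 24) would restore Aim 1 to its planned 80%, and Aim 2 too on the implied SD. The text does not settle this.

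**Conclusion.** The point holds in two parts.

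- **Population.** Operative sections contradict one another on who is studied, and no analysis names diagnosis. The pooled result alone supports neither a DIP-specific conclusion (Aim 1) nor a prodromal-specific one (Aim 2). A reader might go further and call the randomised comparison invalid or pooling wrong. The documents do not support that: the comparison is sound for the mixed population, and pooling is a defensible choice.
- **Sample size.** The statement that 20 per group is adequate for the primary outcomes is unsupported. It holds only in the Aim 2 scenario with a loss of 0.20. If 24 per group is the whole analysis set, Aim 1 power is about 64% (56% at 20). Aim 2 power at 24 is about 87% with no PD and 82/77/70/64% at PD shares of 25/50/75/100% on the implied SD; on the printed SD it runs from 55% to 35%.

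The inconsistency in wording is certain. The Aim 2 figures depend on the assumed PD share, decline rates and SD, and all power figures depend on treating 24 per group as the total.

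**What to change.** 1. Reword Aims 1–3, Hypothesis 1, the Aim 1–2 cohort text in Section 5.1.1 and Section 5.1.3 to the population enrolled. Aim 3 also needs one term, since it says preclinical in Section 4.1 and prodromal in Section 5.1.1. Limit any DIP-specific or prodromal-specific conclusion to that group's own estimate.
2. Report the Aim 1 and Aim 2 effects by diagnosis recorded at entry, with 95% CIs, and the treatment-by-diagnosis interaction, as descriptive only. Give a prodromal estimate only for subjects who meet the Section 5.1.1 definition.
3. Name diagnosis and diagnosis × time in the Aim 2 mixed model. For Aim 1, a diagnosis-adjusted linear model is an optional gain in precision. If adopted, it should be fixed before any comparison by arm.
4. Replace the 20-per-group statement in Sections 5.1.3 and 9.3 with Aim 1 and Aim 2 power at the expected completers for the mixed population. State the assumed PD share, decline rate and SD, and whether the 56 subjects add to those already randomised.

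The cost is low: text changes, named model terms, one descriptive table and a revised power statement. The price in interpretation is that the headline result concerns a mixed population. The estimates by diagnosis will be too imprecise to settle whether the effects differ.
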